#### 3.1 Inclusion Criteria

Participants who meet all of the following criteria are eligible for inclusion in this study:

- Men and women, 18-65 years old at the time of screening
- Willing to provide informed consent for the study
- In the last 12 months (at the time of screening):
  - No unprotected anal or vaginal intercourse with someone known to be HIV-infected or of unknown HIV infection status
  - o No stimulant use (cocaine [including crack], methamphetamine, or non-physician prescribed pharmaceutical-grade stimulants) or inhaled nitrate
  - No illicit injection drug use of any kind
  - o No diagnosis of GC, CT, incident syphilis, bacterial vaginosis, and trichomoniasis
  - Not reporting >= 5 different sexual partners, regardless of use of protection or knowledge of HIV status

Note: "Unknown HIV status" is defined as a partner not known to be HIV infected or HIV uninfected by the potential participant (as assessed by the Investigator of Record or designee). The Clinical Management Committee (CMC) – refer to Section 6.1 for further information regarding the CMC – should be contacted regarding any questions about how to apply or interpret the risk eligibility criteria. The SSP Manual should also be referred to for additional guidance regarding appropriate categorization of participants as low risk.

- In general good health, as evidenced by the following laboratory values, which must be from specimens obtained within 45 days prior to study enrollment:
  - Non-reactive / negative HIV test results\*
  - o Hemoglobin > 11 g/dL,
  - Absolute neutrophil count > 750 cells/mm^3
  - $\circ$  Platelet count  $\geq 100,000/\text{mm}^3$
  - $\circ$  Calculated creatinine clearance  $\geq 70$  mL/minute using the Cockcroft-Gault equation
  - Alanine aminotransferase (ALT) and aspartate aminotransferase (AST) < 2 times the upper limit of normal (ULN)
  - o Total bilirubin < 2.5 times ULN
  - o Hepatitis B surface antigen (HBsAg) negative
  - Hepatitis C Ab negative

\*HIV uninfected, based on HIV test results obtained at Screening and just prior to randomization at the Enrollment visit. All HIV test results from the Screening visit must be obtained and must all be negative/non-reactive. This includes testing for acute HIV infection, which must be performed within 14 days of Enrollment. In addition, at least one HIV test result obtained at the Enrollment visit must be obtained prior to randomization in to the study and must be negative/non-reactive. Individuals who have one or more reactive or positive HIV test results will not be enrolled, even if subsequent confirmatory testing indicates that they are not HIV-infected. Refer to SSP Manual.

- No alcohol or substance use that, in the opinion of the study investigator, would interfere with the conduct of the study (e.g., provided by self-report, or found upon medical history and examination or in available medical records). See Section 3.2 for additional exclusion criteria related to substance use.
- No medical condition that, in the opinion of the study investigator, would interfere with the conduct of the study (e.g., provided by self-report, or found upon medical history and examination or in available medical records)
- Willing to undergo all required study procedures

#### Additional requirements for all women:

- If of reproductive potential (defined as pre-menopausal women who have not had a sterilization procedure per self-report, such as hysterectomy, bilateral oophorectomy, tubal ligation or salpingectomy), **must** have a negative urine pregnancy test performed (and results known) within 48 hours before initiating the protocol-specified medication(s) at enrollment. Women are considered menopausal if they have not had a menses for at least 12 months and have a follicle stimulating hormone (FSH) level of greater than 40 IU/L; if FSH testing is not available, they must have had amenorrhea for 24 or more consecutive months. (FSH testing is not a protocol requirement.)
- If participating in sexual activity that could lead to pregnancy, women must agree to use a form of contraception during the trial and for 30 days after stopping the oral study medication or for 52 weeks after stopping the long acting injectable from the list below:
  - o Condoms (male or female) with or without a spermicidal agent, PLUS a diaphragm or cervical cap with spermicide
  - o Intrauterine device (IUD) or intrauterine system (IUS) that meets <1% failure rate as stated in the product label
  - Hormone-based contraceptive

#### 3.2 Exclusion Criteria

Participants who meet any of the following criteria will be excluded from this study:

- One or more reactive or positive HIV test result at Screening or Enrollment, even if HIV infection is not confirmed
- Co-enrollment in any other HIV interventional research study or other concurrent studies which may interfere with this study (as provided by self-report or other available documentation. Exceptions may be made if appropriate after consultation with the CMC.)
- Past or current participation in HIV vaccine trial. An exception will be made for participants that can provide documentation of receipt of placebo (not active arm).
- Use of ART (e.g., for non-occupational post-exposure prophylaxis [PEP] or PrEP) in the 90 days prior to study entry
- Clinically significant cardiovascular disease, including:
  - o ECG with:
    - heart rate < 45 or > 100 beats per minute for men, and <50 or >100 beats per minute for women (one repeat ECG is allowed during screening; can be performed on the same day)
    - QRS duration >120 msec
    - QTc interval (B or F) > 450 msec
    - evidence of previous myocardial infarction (pathologic Q waves, S-T segment changes (except early repolarization)
    - any conduction abnormality (including but not specific to left or right complete bundle branch block, AV block [2nd degree (type II) or higher], Wolf Parkinson White [WPW] syndrome)
    - sinus pauses > 3 seconds
    - any significant arrhythmia which, in the opinion of the Investigator of Record or designee, will interfere with the safety for the individual participant
    - or history of non-sustained (≥3 consecutive ventricular ectopic beats on ECG at screening or entry) or sustained ventricular tachycardia
  - History/evidence of symptomatic arrhythmia, angina/ischemia, coronary artery bypass grafting (CABG) surgery or percutaneous transluminal coronary angioplasty (PTCA) or any clinically significant cardiac disease
  - Systolic blood pressure at screening outside the range of 90-140 mmHg or diastolic blood pressure is outside the range of 45-90 mmHg (confirmed on repeat measurement)
- Underlying skin disease or currently active skin disorder (e.g., infection, inflammation, dermatitis, eczema, psoriasis, urticaria). Mild cases of localized acne or foliculitis or other mild skin condition may not be exclusionary at the discretion of the Investigator of Record or designee in consultation with the CMC
- Has a tattoo or other dermatological condition overlying the buttock region which in the opinion of the IoR or designee, in consultation with the CMC, may interfere with interpretation of injection site reactions
- Current or chronic history of liver disease (e.g., non-alcoholic or alcoholic steatohepatitis) or known hepatic or biliary abnormalities (with the exception of Gilbert's syndrome, asymptomatic gallstones, or cholecystectomy)

- Coagulopathy (primary or iatrogenic) which would contraindicate IM injection (concomitant anticoagulant or anti-platelet therapy use should be discussed with the CMC)
- Active or planned use of prohibited medications as described in the Investigator's Brochure or listed in the SSP Manual (provided by self-report, or obtained from medical history or medical records)
- Intravenous drug use (episodic, or any use in the past 90 days), or any stimulant use (including cocaine or methamphetamine) in the past 12 months
- For women, pregnant or currently breastfeeding, or intends to become pregnant and/or breastfeed during the study

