#### 744LA dosing:

Following a single IM or SC injection of 744LA, plasma drug concentrations increased rapidly over the first week, followed by a general trend to plateau for the remainder of the 12-week follow-up period. GSK1265744 was detected in plasma up to 48 weeks. When the dose was administered as two equally divided injections, total drug release was increased so that  $C_{max}$  was greater than dose proportional and there was a more pronounced decay in drug concentrations over time. However, overall extent of exposure (AUC $_{0-\infty tau}$ ) was similar. Following single dose 744LA administration, mean absorption-limited apparent terminal phase half-life ranged from 21 to 50 days, reflecting elimination from the depot site (absorption from depot site) rather than the systemic circulation.

744LA PK has been evaluated following repeat administration in healthy HIV-uninfected subjects. Following a loading dose of 800 mg IM and three monthly (every 28 days) maintenance doses, the third monthly 200 mg SC, 200 mg IM and 400 mg IM injections achieved geometric mean plasma  $C_{tau}$  of .61µg/mL, 1.72 µg/mL, and 3.22 µg/mL – 9.7-, 10-, and 19-fold above the PA-IC90 (0.166 µg/mL), respectively. Following two quarterly 800 mg IM doses, geometric mean plasma GSK1265744  $C_{tau}$  was 1.11 µg/mL, 6.7-fold above the PA-IC90.

The rationale for extended follow-up in this study (52 weeks after last injection) is two-fold: The first is to assess safety events during the prolonged interval during which drug levels have been demonstrated to be detectable in blood plasma in order to best characterize the safety profile of 744LA. The second is to characterize in detail any HIV infections which might occur during a period of declining blood plasma drug levels, including viral resistance profiles and response to antiretroviral therapy treatment.

Plans for suppressive ART treatment of on-study incident HIV serconversions are detailed in Section 5.17.

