#### 1.3 Dose Rationale

The 744LA dose rationale is based on the objective to deliver adequate drug concentrations to prevent sexual transmission of HIV. The proposed dose schedule for evaluation in humans is based on maintaining 744LA plasma concentrations well above the PA-IC90 value of 0.166 µg/mL, a concentration range shown to have significant antiviral activity. In a short-term monotherapy study seven HIV-infected subjects received oral 744 5 mg once daily for 10 days, . Geometric mean Day 10  $C_{\tau}$  was 0.57  $\mu$ g/mL, 3.4-fold above the PA-IC90 value, and was associated with a mean Day 11 HIV ribonucleic acid (RNA) change from baseline of -2.2 log10 c/mL. In LAI116482, the Phase IIb study in HIV-1 infected, antiretroviral therapy naïve adult subjects, suppression of HIV infection was accomplished with oral 744 at doses of 10 mg to 60 mg once daily in combination with 2 nucleotide reverse transcriptase inhibitors (NRTIs), and suppression of HIV has been maintained through 24 weeks using a dual regimen of oral 744 and rilpivirine (RPV) at oral 744 10 mg and higher. The geometric mean individual average predose concentration following oral 744 10 mg once daily was 1.35 µg/mL. Following two quarterly doses (12-weeks) of 744LA 800 mg IM in healthy subjects, geometric mean (trough concentration)  $C_{\tau}$  was approximately 1.11 µg/mL, approximately 6.7-fold above the PA-IC90 and between the 5 mg and 10 mg oral doses (Table 1). Furthermore, based on population PK modeling and simulation, 744LA 800 mg IM every 12 weeks achieves a mean concentration above the 1.35 µg/mL target based on 10 mg daily oral dosing and the lower bound of the 90% confidence interval (CI) is at 4-fold PA-IC90 (Figure 1). The overall range in predicted 744LA  $C_{\tau}$  values following 744LA 800 mg IM is similar to that following once daily dosing of oral 744 10 mg (Figure 2).

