#### 1.4 Clinical Experience to Date – GSK1265744

As of June 30, 2013, 483 adult subjects have been exposed to at least one dose of GSK1265744 in sponsored Phase I-IIb clinical trials. GSK1265744 has been evaluated in ten Phase I/IIa clinical pharmacology studies (eight studies in healthy HIV-uninfected subjects; one study in healthy HIV-uninfected subjects and HIV-infected subjects; and one study in HIV-infected subjects only), as well as one Phase IIb clinical study utilizing oral 744. Four studies are currently ongoing (3 Phase I studies and 1 Phase IIb study).

Oral 744 has been studied at doses between 5 mg - 150 mg in HIV-uninfected and HIV-infected adults. The oral formulation of GSK 1265744 has been generally well-tolerated as single or repeated doses in clinical studies of HIV-uninfected adults. Among the HIV-uninfected and HIV-infected subjects who received oral formulations ranging from 5 mg-150 mg in Phase 1 and 2a studies, three subjects receiving oral 744 were withdrawn due to drug-related adverse events (AEs), including dizziness, leucopenia, and aspartate aminotransferase and alanine aminotransferase [AST/ALT]/gamma-glutamyltransferase increase. No drug-related Grade 3 or Grade 4 AEs or serious adverse events (SAEs) were reported 46.

In total, 136 HIV-uninfected subjects have received single or repeat doses of 744LA 100-800 mg IM or subcutaneous (SC) injections alone or in combination with long acting RPV (TMC278 LA). To date there have been no drug-related Grade 3 or Grade 4 AEs or SAEs and only one subject withdrew due to an AE (self-limited Grade 1 rash) following 744LA. Two non-drug related SAEs have been reported: foot osteomyelitis and elective hysterectomy. Injection site reactions (ISR) occurred in the majority of subjects following IM (76% with any ISR) dosing, however, the reactions were mild and moderate (overall ISR Grade 2: 14% in IM without any Grade 3 or 4 ISRs). ISRs related to 744LA injection were common but generally mild (IM: 86%, SC: 99%) with no Grade 3 ISR AEs. The most frequent ISRs for IM dosing were pain (71%), erythema (9%) and nodules (7%)C 2013). Median IM ISR durations were approximately 5 days for pain and erythema, and approximately 22 days for nodules.

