### 2.4 Study Design and Overview

This is a Phase IIa, randomized, multi-site, two-arm, double-blind study of the safety, tolerability, pharmacokinetics, and acceptability of 744LA. Eligible participants will begin an oral lead-in phase in which they will be randomized to receive daily oral 744 (30 mg tablets) or matching placebo for 4 weeks, followed by a one week washout period, to assess safety prior to receiving 744LA. Following final safety lab assessments from the oral regimen phase, participants will enter the injection phase and receive IM injections of 744LA or placebo at three time points at 12 week intervals. IM injections will consist of 800 mg of 744LA or a matching vehicle control, administered as two (2) 400 mg split injections.

176 participants will be randomized 3:1 as follows:

Arm 1: 132 participants will receive daily oral 744 (30 mg tablets) for 4 weeks, followed by a one week washout period, to establish safety and tolerability, followed by intra-muscular (IM) gluteal injections of 800 mg of 744LA (administered as two sequential 400 mg gluteal injections) at three time points at 12 week intervals as: Week 5, Week 17, and Week 29.

Arm 2: 44 participants will receive daily oral matching placebo and IM injections of vehicle-matched placebo on the same schedule as Arm 1.

All participants will receive HIV testing with pre- and post-test counseling, in addition to risk-reduction counseling and condoms and lubricant. All participants will be followed according to the Schedule of Evaluations and Procedures provided in Appendices I-IV.

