### 3.0 STUDY POPULATION

One hundred seventy six (176) HIV-uninfected men and women will be included in this study. A parallel study is being conducted in the US in men who have sex with men; as such, this study aims to enroll a higher proportion of women (60%). Each site will be asked to work with their community advisory boards (CABs) and outreach, education and recruitment teams to develop a recruitment plan appropriate for their local population. Participants will be selected for the study according to the criteria in Sections 3.1 and 3.2. Study participants will be recruited as described in Section 3.3 and assigned to a study arm as described in Section 7.5. Requirements related to participant retention and withdrawal from the study are described in Sections 3.5 and 3.6, respectively. Individual sites will be given enrollment targets and gender distribution targets commensurate with study population needs, adjusted for local epidemiology, such that overall cross-site enrollment meets overall protocol goals. Enrollment targets may be substantially different in terms of gender distribution across sites.

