#### Pharmacology

Plasma samples for drug levels will be collected beginning at Week 2 through and including the last study visit at Week 81. These samples will collected from all participants, although PK testing may be limited to a subset of the samples.

Plasma will be processed and frozen locally for subsequent shipment to the HPTN LC following procedures outlined in the SSP Manual. Pharmacology testing will be performed at the HPTN LC or at an outside laboratory designated by the HPTN LC. The primary pharmacologic assessments will be performed using assays that have been validated and approved by the Clinical Pharmacology Quality Assurance (CPQA) Committee. Results will not be returned to the sites or study participants.

NOTE: Samples may be unblinded in the HPTN Pharmacology Laboratory (only), so the relevant assays are only performed on participants who received the study product.

Stored plasma may also be tested for the presence of other ARV drugs or other substances.

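### The 90-day ART exclusion is only 6 days longer than one 744LA dosing interval, so a person who received 744LA in a study they have left or been exempted from could be randomised with drug on board

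*Protocol*

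**What the plan says.** Section 3.2 excludes "Use of ART (e.g., for non-occupational post-exposure prophylaxis [PEP] or PrEP) in the 90 days prior to study entry". This is the only time limit on past antiretroviral use. The neighbouring bullets on research participation cover two cases: co-enrolment in other studies, where the Clinical Management Committee (CMC) may make exceptions, and HIV vaccine trials, past or current, with an exception for documented placebo. Section 3.4 also bars concurrent studies. The prohibited-medication bullet concerns active or planned use, and Section 4.4 records concomitant medication only from 30 days before enrolment.

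On the drug itself, injections are given "at three time points at 12 week intervals as: Week 5, Week 17, and Week 29" (Section 2.4). Section 1.2.4 reports that the geometric mean trough after two quarterly 800 mg IM doses "was 1.11 µg/mL, 6.7-fold above the PA-IC90", gives a half-life of 21 to 50 days after a single dose, and states that "GSK1265744 was detected in plasma up to 48 weeks". Section 1.3 bases the dose on a PA-IC90 "value of 0.166 µg/mL, a concentration range shown to have significant antiviral activity". Active-arm participants are followed for 52 weeks after the last injection because of this tail (Sections 1.2.4 and 2.4.2), and Section 3.1 asks for contraception over the same 52 weeks.

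On who may already have been exposed, Section 1.4 says that "136 HIV-uninfected subjects have received single or repeat doses of 744LA", counted to 30 June 2013. Section 3.0 adds that "A parallel study is being conducted in the US in men who have sex with men". On detection, Section 9.2 says "Plasma samples for drug levels will be collected beginning at Week 2", and Sections 7.5 and 9.2 let the pharmacology laboratory assay only participants on active product.

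**The concern.** A look-back of 90 days, with oral PEP and PrEP as its examples, suits oral drugs. It is no washout for a product designed to be active 84 days after injection. The Protocol treats exposure as lasting about a year everywhere except in this criterion. A site that did not read investigational 744LA as ART would have no time limit at all.

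A prior recipient assigned to placebo would be a drug-exposed control in an arm of 44. One assigned to 744LA would start from a non-zero baseline. That would raise the first-injection AUC, Cmax and Cτ, which Table 7 uses as the reference for accumulation, so accumulation would be understated for that person. The oral lead-in would also no longer be a first test of individual tolerability.

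**Working it through.** **Inputs.** ART window 90 days (Section 3.2). Dosing interval 12 weeks = 84 days (Section 2.4). Trough 1.11 µg/mL, N=9, CV 139% (Table 1). PA-IC90 0.166 µg/mL (Section 1.3). Half-life t of 21 to 50 days (Section 1.2.4).

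**Reproducing the stated figure.** 1.11 / 0.166 = 6.69, which rounds to the stated 6.7.

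**Window against interval.** 90 − 84 = 6 days; 90 / 84 = 1.07 intervals.

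**Level d days after the last injection**, assuming log-linear decay from the day-84 trough: C(d) = 1.11 × 2^(−(d − 84)/t).

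| Time point, if enrolled at day 90 | d | C at t = 21 (µg/mL) | C at t = 50 (µg/mL) | Multiple of PA-IC90 |
|---|---|---|---|---|
| Enrolment | 90 | 0.91 | 1.02 | 5.5 to 6.2 |
| First study injection (Week 5) | 125 | 0.29 | 0.63 | 1.7 to 3.8 |
| First Cτ (Week 17) | 209 | 0.02 | 0.20 | 0.1 to 1.2 |

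The geometric mean reaches the PA-IC90 at 84 + t × log2(1.11/0.166), about day 142 (t = 21) to day 221 (t = 50).

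**Check against the Protocol's own simulation.** Table 1 gives 1.57 µg/mL on schedule and 1.41 µg/mL with a one-week delay. The decay rate is ln(1.57/1.41)/7 per day, a half-life of 45 days. Applied to 1.11 for 6 days it gives 1.01 µg/mL, or 6.1 times the PA-IC90.

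**Other regimens.** Section 1.2.4 gives troughs after monthly dosing. Day 90 is 62 days after a day-28 trough, so the multiple is (trough/0.166) × 2^(−62/t):

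- 200 mg SC (1.61 µg/mL, inferred from the stated 9.7-fold): 1.3 to 4.1
- 200 mg IM (1.72 µg/mL): 1.3 to 4.4
- 400 mg IM (3.22 µg/mL): 2.5 to 8.2

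**Recipients in the June 2013 count.** The Protocol cites a paper dated 7 March 2014, so entry is at least 250 days after any dose counted to 30 June 2013. C(250) is 0.005 to 0.11 µg/mL, or 0.03 to 0.67 times the PA-IC90.

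**Could the Week 5 pre-injection sample show carry-over?** Assume dose-proportional oral PK and a 30 mg trough of 3 × 1.35 = 4.05 µg/mL. With the 40-hour oral half-life, one week of washout (168/40 = 4.2 half-lives) leaves 4.05 × 2^(−4.2) = 0.22 µg/mL. Carry-over of 0.29 to 0.63 µg/mL is of the same order, so this sample does not separate the two cleanly in the active arm.

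**Weight of one person.** 1/44 = 2.3% of the placebo arm; 1/132 = 0.8% of the active arm.

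**The case against.** The case against giving this much weight is strong, and most of it stands.

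- **Parallel study.** A reader might infer that anyone in the parallel US study could walk in at day 90. Sections 3.2 and 3.4 exclude people still enrolled in another interventional study. The route is open only to someone who has left, or who receives a CMC exception under Section 3.2. The parallel study's dose and follow-up are not given.
- **The 136 recipients.** A reader might count all of them as at risk. By the decay formula above, doses in that count would have fallen below the PA-IC90 on average. Only doses given after the cut-off, in studies then still running, could be recent enough to matter.
- **The multiple.** About 6 times is a geometric mean for one regimen in nine people with a CV of 139%. It is not a general figure.
- **Detection.** It would go too far to say that carry-over could not be found. Plasma is stored at Screening and Enrollment (Sections 5.1 and 5.2), and Section 9.2 allows stored plasma to be tested for other antiretrovirals. Pre-dose samples therefore exist; what is missing is a planned assay.
- **Bias.** A reader might infer that both primary proportions lean toward safety. The Protocol does not establish this. A prior recipient may be a selected tolerator, but a drug-exposed placebo participant could equally have more adverse events. The arms are not formally compared, and at an observed 5% rate Table 4 gives a placebo interval of 1.4% to 16.5%, so a shift of at most 2.3 points is small.
- **Other safeguards.** The full medical history, CMC advice on eligibility and the prohibited-medication list might catch such a person. They are discretionary or not shown, and none is a stated bar.

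What remains is that no criterion in Sections 3.1, 3.2 or 3.4 excludes a person who received 744LA and has since left that study.

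**Conclusion.** The gap is real but minor. The 90-day rule is not a washout for a long-acting injectable: on the Protocol's figures it admits a prior recipient at about 5.5 to 6.2 times the PA-IC90 after two 800 mg IM doses, or roughly 1.3 to 8.2 times after the monthly regimens. These figures assume log-linear decay at the stated half-lives and describe averages, with wide variation between people.

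The number of such enrollees is not given, is probably very small and may be zero. If one occurs, the damage is a contaminated placebo participant (2.3% of that arm) or a raised first-interval reference for accumulation, without a planned assay to reveal it. The Protocol supports neither a claim of material bias in the primary safety or tolerability proportions nor a direction for it.

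**What to change.** Add to Section 3.2 an exclusion for prior receipt of 744LA or another long-acting injectable antiretroviral, with an exception for documented placebo like the one already written for vaccine trials. Add one screening question to match. Keep the 90-day rule for oral ART.

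If the sponsor wishes to admit prior recipients, it should reconcile the 90-day window with the Protocol's own statements on 48-week detectability and the 52-week tail. No particular washout is proposed here.

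The cost is one eligibility line, one question and the loss of a few otherwise eligible people.
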